Statistical Analysis Plan (SAP)

Principal Investigator	[name] Professor of Gerontology, Psychology and Biomedical Engineering University of Southern California Los Angeles, California, USA
Protocol identification number	UP-17-00219
ClinicalTrials.gov identifier	NCT03458910
Author	[name] Research Associate [name] of Southern California Los Angeles, California, USA
Version	Draft 0.2
Date	09/09/2024

1. Objectives and hypotheses

The main objective of the study was to test the hypothesis that daily biofeedback sessions stimulating heart rate oscillatory activity in baroreflex frequencies affect the function of brain networks involved in emotion regulation. Our main outcome measure was pre-to-post intervention changes in resting-state right amygdala functional connectivity with a medial prefrontal cortex region associated with heart rate variability (HRV). Our secondary outcome measures were pre-to-post intervention changes in up- and down-regulation of amygdala activity and self-reported emotion regulation effectiveness during viewing emotional pictures, as well as changes in ratings of emotional well-being. Other secondary outcome measures included HRV during rest, measures of cerebral blood flow, decision making, stress responsivity and cognitive performance. As a post-hoc outcome measure, we examined pre-to-post intervention changes in resting-state left amygdala functional connectivity with a medial prefrontal cortex region.

2. Sample Size & Power consideration

121 younger adults and 72 older adults participated in the study.

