No prior studies had examined effects of these interventions on brain function so we were unable to estimate effect sizes based on prior neuroimaging data. We elected to power our study to detect medium or larger effect sizes. Our main planned statistical comparisons were repeated-measures ANOVAs with within-between interactions. For these, a total sample size of 46 would give 90% power to detect moderate effect sizes of $f=.25$ with $\alpha = .05$, given an assumed correlation among the repeated measures of .5 (Faul et al., 2007). We also planned to examine within-subject change within each of the conditions. A sample size of 44 in each condition (HRV-increase, HRV-decrease) would give 90% power to detect within-group change effect sizes of $d=.5$ in a two-tailed t-test with $\alpha = .05$ (Faul et al., 2007). Thus, we aimed for an N=200 completion rate across the two conditions and two age groups to be able to accommodate potential exclusions for movement during imaging or other data quality issues. Due to the COVID-19 pandemic leading to increased risk for participants completing lab visits, we terminated the study before achieving our initial goal of recruiting 100 older participants.

3. Outcomes

For most outcome measures, we examined group difference (HRV-increase vs. HRV-decrease) in pre-post intervention change. The average time between pre and post intervention assessment was 5 weeks.

Primary outcome measures

- Group difference in pre-post intervention change in resting state functional connectivity between the right amygdala and medial prefrontal cortex (mPFC)

Secondary outcome measures

- Group difference in pre-post intervention change in:
 - Emotion regulation ability measured by self-reported effectiveness when instructed to regulate emotion during viewing emotional pictures
 - The ability to up- and down-regulate amygdala activity when instructed to regulate emotion during viewing emotional pictures
 - Emotional well-being measured by the Profile of Mood States (POMS), the State Anxiety Inventory (SAI), the Trait Anxiety Inventory (TAI) and the Center for Epidemiologic Studies (CES-D)
 - HRV measured by high frequency power (HF)
 - HRV measured by low frequency power (LF)

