 - HRV measured by the root mean square of successive differences (RMSSD)
 - Inflammatory markers including C-reactive protein, IL-1b, IL-6, IL-8 and TNF-a
 - Stress recovery
 - Stress reactivity
- Group difference in cerebral blood flow during pre-intervention resting state and post-intervention paced-breathing
- Group difference in decision-making ability measured by multiple-choice responses during a computer-based decision-making task at the post-intervention MRI
- Group difference in the ability to up- and down-regulate task-relevant brain regions during a computer-based decision-making task at the post-intervention MRI

Other outcome measures

- Group difference in pre-post intervention change in:
 - Working memory measured by NIH Toolbox List Sorting Working Memory Test (LSWM)
 - Processing speed measured by NIH Toolbox Pattern Comparison Processing Speed Test (PCPS)
 - Inhibitory control and attention measured by NIH Toolbox Flanker Inhibitory Control and Attention Test (Flanker)
 - Sustained attention measured by Sustained Attention to Response Test (SART)
 - Stress measured by cortisol levels
- Group difference in recognition memory after about three and half weeks of training
- Group difference in recall memory after about three and half weeks of training

Safety outcomes

No adverse events were observed.

4. Populations and subgroups to be analyzed

Population analyzed is composed by all randomization subjects who completed assessments and whose data quality was sufficient for data analysis.

5. Analyses

Primary outcome measures

- Resting state functional connectivity between the right amygdala and medial prefrontal cortex (mPFC): We performed a 2 (time point: pre, post) \times 2 (condition: HRV-increase, HRV-decrease) mixed ANOVA. The effect of interest was a time \times condition interaction, and P values less than 0.05 were considered statistically significant.

Secondary outcome measures

- Emotion regulation (behavioral analysis):

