We conducted a three-way ANOVA to examine whether emotional intensity rated by participants during emotion regulation changed after HRV biofeedback intervention for younger and older adults separately. The 2 \times 2 \times 3 ANOVA model included three factors: time-point (2 levels: pre- and post-intervention), intervention condition (2 levels: HRV-Increase, HRV-Decrease) and regulation type (3 levels: down-regulation, viewing and up-regulation). P values less than 0.05 were considered statistically significant.
- Emotion regulation (MRI analysis):
We conducted a three-way ANOVA to examine whether BOLD activity in the left and right amygdala changed during emotion regulation after HRV biofeedback intervention for younger and older adults. The 2 \times 2 \times 3 ANOVA model for each amygdala included three factors: time-point (2 levels: pre- and post-intervention), intervention condition (2 levels: HRV-Increase, HRV-Decrease) and regulation type (3 levels: down-regulation, viewing and up-regulation). P values less than 0.05 were considered statistically significant.
- Emotional well-being (pre/post):
To test whether emotional well-being changed during the course of the study and whether this depended on training condition, we performed a series of two-way mixed ANOVAs, one for each measure. In these ANOVAs, time was a within-subjects factor (2 levels: pre- and post-intervention) and condition was a between-subjects factor (2 levels: HRV-Increase, HRV-Decrease). For each ANOVA, the effect of interest was a time \times condition interaction, and only data from participants with values for both time points were included. P values less than 0.05 were considered statistically significant. ANOVAs were performed with R (Version 4.0.3) and the R package 'ez'.
- Emotional well-being (all weeks):
To test whether emotional well-being changed during the course of the study and whether this depended on training condition, we fit a series of linear mixed effects models, one for each measure. For these models, fixed effects were time (1 level per week), condition (2 levels: HRV-Increase, HRV-Decrease), and a time \times condition interaction. The models included random intercepts for participants. For each model, data from all available participants at each time point was used. To assess parameter significance, F- and p-values were determined using Satterthwaite's method. P values less than 0.05 were considered statistically significant. These

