analyses were performed with R (Version 4.0.3) and the R packages 'lmer4' and 'lmerTest'.

- HRV measured by high frequency (HF) HRV, low frequency (LF) HRV and the root mean square of successive differences (RMSSD):
To test whether HRV changed during the course of the study and whether this depended on training condition, we performed a series of two-way mixed ANOVAs, one for each measure. In these ANOVAs, time was a within-subjects factor (2 levels: pre- and post-intervention) and condition was a between-subjects factor (2 levels: HRV-Increase, HRV-Decrease). For each ANOVA, the effect of interest was a time x condition interaction, and only data from participants with values for both time points were included. P values less than 0.05 were considered statistically significant. ANOVAs were performed with IBM SPSS statistics (Version 27) and R (Version 4.0.3) with R package 'ez'.
- Inflammatory markers:
For each inflammatory marker (IL-1b, IL-6, IL-8, TNF-a, CRP), we conducted a two-way ANOVA to examine whether its levels changed after HRV biofeedback intervention for younger and older adults separately. The 2 x 2 ANOVA model included two factors: time-point (2 levels: pre- and post-intervention) and intervention condition (2 levels: HRV-Increase, HRV-Decrease). P values less than 0.05 were considered statistically significant.
- Recovery from stress:
To test whether stress recovery changed during the course of the study and whether this depended on training condition, we performed a series of two-way mixed ANOVAs, one for each measure of stress recovery. In these ANOVAs, time was a within-subjects factor (2 levels: pre- and post-intervention) and condition was a between-subjects factor (2 levels: HRV-Increase, HRV-Decrease). For each ANOVA, the effect of interest was a time x condition interaction, and only data from participants with values for both time points were included. P values less than 0.05 were considered statistically significant. ANOVAs were performed with R (Version 4.0.3) and the R package 'ez'.
- Reactivity to stress:

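### At least 42 secondary and other tests are each called statistically significant at an unadjusted P<0.05, so about two false positives are expected if the two arms differ on none of these outcomes

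*SAP*

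**What the plan says.** SAP Section 3 names one primary outcome, the group difference in change in right amygdala–mPFC connectivity, and ranks the rest as secondary or other. Section 5 describes eleven secondary and five other analyses, and each carries the sentence "P values less than 0.05 were considered statistically significant".

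Several of these analyses cover more than one test:

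- Emotion ratings are modelled by age group: "emotional intensity rated by participants during emotion regulation changed after HRV biofeedback intervention for younger and older adults separately".
- The imaging counterpart uses one model per amygdala: "BOLD activity in the left and right amygdala changed during emotion regulation after HRV biofeedback intervention for younger and older adults". It does not say that the age groups are analysed separately.
- The four well-being scales are each analysed twice, by a pre/post ANOVA and by an all-weeks mixed model.
- Inflammation has five markers, again by age group: "For each inflammatory marker (IL-1b, IL-6, IL-8, TNF-a, CRP), we conducted a two-way ANOVA to examine whether its levels changed".
- Stress recovery is a series of ANOVAs, "one for each measure of stress recovery", with the number of measures not given. Stress reactivity is described in the same way.

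Section 1 calls left amygdala connectivity post hoc. No such label is attached to any secondary or other outcome. Section 1 also places cognition in the secondary tier ("Other secondary outcome measures included HRV during rest, measures of cerebral blood flow, decision making, stress responsivity and cognitive performance"), whereas Section 3 lists the NIH Toolbox tests under other outcomes.

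**The concern.** The 0.05 rule describes the error of one test. Many of the listed outcomes are domains examined by several tests, and the SAP does not say how many hits, or which ones, would support a statement about the domain. A report that training changed inflammation could rest on one marker in one age group, out of ten tests. A report about well-being could rest on one of eight. The chance of a false statement at that level is not 5%, and nothing in the plan tells a reader what it is.

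The two placements of cognition add to the difficulty, because the tier is then no guide to the weight of a cognitive result. That is a wording conflict only: both tiers use 0.05, so it changes neither the count nor the error rate.

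**Working it through.** **The plan's own figures.** The SAP states no family-wise or overall error figure. Its only related numbers are the sample sizes in Section 2, both set at α = 0.05 for a single test, and both reproduce.

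- Interaction: λ = f²·N·m/(1−ρ) = 0.0625 × 46 × 2/0.5 = 11.5 on 1 and 44 df gives power 0.912. N = 44 gives 0.8997, so 46 is the smallest even total.
- Within-group change: a paired t-test with n = 44 and d = 0.5 gives power 0.900.

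**Count of tests (SAP Section 5, one focal effect per model).**

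| Tier | Analysis | Tests |
|---|---|---|
| Secondary | Emotion ratings, 2 age groups | 2 |
| | Amygdala activity, left and right | 2 |
| | Well-being pre/post, 4 scales | 4 |
| | Well-being all weeks, 4 scales | 4 |
| | HRV: HF, LF, RMSSD | 3 |
| | Inflammation, 5 markers × 2 age groups | 10 |
| | Stress recovery and reactivity, at least 1 each | 2 |
| | Cerebral blood flow | 1 |
| | Decision-making, 2 behavioral + 2 MRI | 4 |
| | **Subtotal** | **32** |
| Other | Cognition 3, SART 2, cortisol 1, recognition 2, recall 2 | **10** |
| | **Total** | **42** |

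The count is low in three respects. It takes one effect per model, although a 2 × 2 × 3 ANOVA has four effects involving condition and several models name no effect of interest. It takes one measure each for stress recovery and reactivity. It does not split the amygdala models by age.

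**Expected false positives with no between-arm difference on any outcome.** Count × 0.05, which holds under any correlation:

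- 42 × 0.05 = 2.1
- 32 × 0.05 = 1.6 (secondary tier alone)
- 38 × 0.05 = 1.9 (without the all-weeks well-being models)
- 33 × 0.05 = 1.65 (no age split anywhere)
- 44 × 0.05 = 2.2 (amygdala models also split by age)
- 65 × 0.05 = 3.25 (every model except cortisol split by age)

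**Chance of at least one.** If independent, 1 − 0.95⁴² = 0.884. For two-sided normal test statistics with a common correlation r, the chance of none is the average over a standard normal u of [Φ((1.96−√r·u)/√(1−r)) − Φ((−1.96−√r·u)/√(1−r))]⁴². The documents give no correlations, so r is assumed:

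| r | 0 | 0.3 | 0.5 | 0.7 |
|---|---|---|---|---|
| 42 tests | 88% | 76% | 58% | 38% |

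**Inflammation.** If the ten tests are independent, 1 − 0.95¹⁰ = 0.401. Younger and older adults are different people, so correlation applies only within each block of five. At r = 0.3 the chance of no hit in one block is 0.791, and 1 − 0.791² = 0.374.

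**Power cost of adjustment.** Take one true effect with 90% unadjusted power (mean z = 1.96 + 1.28 = 3.24), all other family members null, and r = 0.3. By simulation, Holm and Benjamini-Hochberg agree to within a percentage point:

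| Family size | 3 (HRV) | 4 (emotion regulation; decision-making) | 8 (well-being) | 10 (inflammation) |
|---|---|---|---|---|
| Power | 80% | 77% | 70% | 67% |

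**The case against.** The SAP has one primary outcome and ranks everything else below it. That ranking is itself a limit on interpretation, and the primary test keeps its 5% error. Leaving lower tiers unadjusted and reading each test on its own is common practice, and for a claim about one named marker 0.05 is the per-test error. The SAP states no domain-level success rule; the inflammation and well-being statements imagined above are not in it. All of this stands, and it is why a mandatory correction is partly a trade-off. It does not explain why unadjusted lower-tier results are called statistically significant with no exploratory label, when the same SAP marks left amygdala connectivity as post hoc.

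A reader might infer that 2.1 is the number of false claims expected if training does nothing. The documents do not support that wording. Both arms train, and where the SAP names an effect of interest it is time by condition. The null is therefore no difference between two trained arms on any of the 42 tests, including resting HRV, although the arms are trained to move HRV in opposite directions. The figure is a reference case, not a forecast. If the arms differ on some outcomes, fewer false positives are expected.

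A reader might also take 88% as the chance of a false claim. That needs independent tests, and these come from the same participants, with well-being analysed twice.

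Finally, the SAP is dated 09/09/2024 and written in the past tense, so families named now are retrospective. That stands, and the fix has to say so.

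**Conclusion.** The point holds as a reporting weakness in the secondary and other tiers. At least 42 tests are each called significant at an unadjusted 0.05, with about 2.1 false positives expected if the arms differ on none of these outcomes. The expectation does not depend on correlation; about half of any such false positives would favor the HRV-increase arm. The chance of at least one does depend on correlation and is best given as a range, from 88% down to 38% for r between 0 and 0.7. For inflammation it is 40% if independent and 37% at r = 0.3 within each age group.

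The conclusion does not hang on the other tier, since the 32 secondary tests alone give 1.6. A reader might infer that the trial's main result is compromised. It is not: the primary test is outside the 42 and its error rate is unchanged.

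**What to change.** Keep the primary at 0.05.

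For the secondary outcomes:

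1. Group the tests by the SAP's own outcome headings: emotion regulation, well-being, HRV, inflammation across both age groups, stress, decision-making. Blood flow stands as its own single-test family.
2. State that the grouping is retrospective.
3. Show Holm or Benjamini-Hochberg adjusted P values beside the raw ones.
4. Reserve the term statistically significant for adjusted results.
5. List the stress recovery and reactivity measures, so that the size of that family is known.

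Report the other outcomes as exploratory, with estimates and confidence intervals. Reconcile the tier of cognition between Sections 1 and 3.

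If the sponsor prefers no adjustment, the minimum is to label all secondary and other results exploratory and drop the term.

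The work is SAP wording and one extra column of P values; no new data are needed. The downside is the loss of power for a lone effect tabulated above, largest for well-being and inflammation. Showing the raw P values as well keeps that information in view.
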